14.7.4 Data Verification and Review

All eCRFs will be subjected to automated and manual validation checking for omitted data, gross data inconsistencies, and timeliness of reporting. Biosense Webster, Inc. will employ a clinical trials database on a server, available to site and sponsor personnel over an Internet connection. Periodic analysis of each data field (across cases) will be performed in order to examine the expected distributions of data, and to identify outliers for possible data entry errors.

14.7.5 Final Data Analysis

All exported datasets for analyses will undergo a final data review prior to final database lock. Once all critical data are monitored and locked, the final analyses of study data will be performed.

14.7.6 Confidentiality and Protection of Study Data

To ensure confidentiality, protection, and attribution of the clinical study data, only trained and authorized sponsor and site personnel will be assigned unique user accounts and passwords to access the clinical trial database. Each user account is designed to allow appropriate user rights and access level with the clinical trials database system.

14.7.7 Publication Policy

Publication of study results will be coordinated between Biosense Webster, Inc. and the Physician Advisory Committee members. Authorship will be determined by Biosense Webster prior to development of any manuscript.

15.0 Study Management

15.1 Sponsor Responsibilities

The Sponsor (Biosense Webster, Inc. or an appropriately qualified and trained designee (ie, a CRO that has been contracted by Biosense Webster, Inc. to assist with study management) will be responsible for the following:

- Investigator selection
- Inform investigator of his/her responsibilities
- Selection of members of the Physician Advisory Committee (PAC) and the Global Safety Monitoring Committee (GSMC)
- Ensure that appropriate training/information is provided to the study investigators and staff
- Obtain study contracts with investigators/hospitals, CROs and other involved parties
- Preparing (and modifying, if needed) study documents including but not limited to the protocol, eCRFs and ICF template
- Completing pre-study site assessments and approvals
- Monitoring the study throughout its duration
- Database input, management and maintenance
- Conducting all communications to applicable authorities
- Informing Investigators of their responsibilities
- Preparing reports summarizing the status of the clinical study which will be supplied to the Principal Investigator at each site
- Ensure that all AEs are reported by the study investigators and where appropriate, are reported to the other investigators and relevant regulatory authorities

15.2 Investigator Selection

Biosense Webster will select investigators qualified by education, training, and experience to assume responsibility for the proper conduct of the trial. Furthermore, each investigator is expected to make a self assessment of his/her qualifications after considering the study protocol and demands of the study. The investigator's signature on the Protocol signature page constitutes an affirmative assertion that he/she is qualified to conduct the study and constitutes the investigator's commitment to abide by the study protocol requirements.

15.3 Investigator Training

Training of appropriate clinical site personnel will be the responsibility of the Sponsor. To ensure uniform data collection and protocol compliance, Sponsor personnel or designee will present to the study site personnel including but not limited to reviewing the applicable Good Clinical Practice (GCP) guidelines, the protocol, the case report form and data collection process, randomization process, and the safety and complaint reporting processes.

15.4 Investigator Responsibilities

- Work with CRO to obtain IRB/EC approval
- Provide the Sponsor with:
 - Annual IRB (or equivalent, eg, EC/EB) approval letters and IRB (or equivalent, eg, EC/EB) approved consent forms
 - Fully executed Clinical Study Agreement
 - Completed Financial Disclosures
 - Curriculum vitae for Investigator(s) and relevant study staff
 - Copy of the annual report to the EC/IRB from the investigator
- Completing the appropriate training the study protocol prior to enrolling and treating subjects
- Obtain informed consent form and enroll patients
- Perform medical procedures per protocol
- Order all tests required by the study protocol
- Adhere to the study protocol
- Follow subjects until the end of the study protocol
- Complete eCRFs on time, completely and accurately
- Allow the Sponsor direct access to source documents to perform monitoring duties, and to perform audits
- Maintain records and provide reports according to the local legislation/regulations
- Share all relevant study-related information with colleagues involved in this study
- Inform the appropriate entities (eg, Sponsor, Biosense Webster, Inc.'s Complaints Management Department, the EC / EB) in a timely manner regarding the occurrence of any AEs

At a minimum, the records listed below are to be maintained by the investigator:

- Study protocol and all amendments
- Signed Clinical Study Agreement
- IRB/EC approval letter, including approved ICF document
- IRB/EC membership list
- Correspondence relating to the study
- CVs for all investigator(s)
- Site personnel delegation of authority/responsibility
- Clinical Monitor/Site Visit sign-in log
- Subject enrollment log
- Lab certification and lab test normal ranges (pregnancy test, INR)
- Reports (e.g. annual reports, final reports from investigator and Sponsor)

The following records must be maintained for each subject enrolled in the study:

- Signed patient ICF
- All completed CRFs and supporting source documentation
- Supporting documentation of any AEs and/or death

The investigator must retain copies of procedure reports, procedure nursing notes and the results of any interventional procedures that occur while the subject is enrolled in the study. Biosense Webster reserves the right to secure data clarification and additional medical documentation on subjects enrolled in this study.

15.5 Physician Advisory Committee (PAC)

The responsibilities of the PAC include:

- Consultation on study design, protocol development, and investigator training
- Ensure investigators compliance with the protocol
- Provide support regarding emergent issues:
 - Advising the Sponsor of any unforeseen medical issues identified during the clinical study
 - Addressing patient medical concerns or conditions raised by investigators as related to the use of the continuation/discontinuation of OAT
- Review of evidence results (assist in data interpretation)
- Publication Committee (strategy and consultation)

15.6 Global Safety Monitoring Committee (GSMC)

All AEs will be monitored until they are resolved or explained. Each AE will be reported regardless of severity, outcome, or causality. To minimize risks to subjects enrolled in the clinical investigation, the sponsor will convene a formal Global Safety Monitoring Committee (GSMC) to review the safety data and recommend appropriate action(s) to ensure subject safety.

The GSMC is tasked with adjudicating severity and causality of adverse events. Activities related to the collection of source documentation and narrative writing for events presented for adjudication by the GSMC will be performed by the sponsor or designee. In addition to reviewing individual adverse events, the GSMC may also review the accumulated safety data for the clinical investigation. Sponsor or designee will collect and compile the information packets or listings for the GSMC to review. Biosense Webster will manage the GSMC.

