8.0 Pilot Study Plan

8.1 Study Design

This is a prospective, multicenter, randomized (1:1), controlled, two-arm, unblinded, pilot study, evaluating the incidence of thromboembolic and hemorrhagic complications after withdrawal of OAT compared to continuation of OAT in subjects who have undergone successful cardiac ablation.

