10.0 Study Endpoints

10.1 Primary Endpoint

The primary endpoint is a composite endpoint represented by the occurrence of any major thromboembolic event (stroke [i.e., ischemic, hemorrhagic or cryptogenic] that is an acute onset of a focal neurologic deficit of presumed vascular origin lasting for ≥ 24 hours or resulting in death) or major hemorrhagic complication (major bleeding) during the 12-month Evaluation Period.

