12.4 Outcome

Regarding the outcome of each AE, the investigator will assess and evaluate the relationship according to the following classifications:

Table 6: Adverse Event Outcome Classifications

Classification	Definition
Resolved without sequelae	Subject fully recovered with no observable residual effects
Resolved with sequelae	Subject recovered with observable residual effects
Improved	Subject's condition improved, but residual effects remain
Unchanged	AE is ongoing
Worsened	Subject's overall condition worsened
Death	Subject died as a result of the AE

12.5 Adverse Event Documentation and Reporting Requirements:

AE information will be collected throughout the study and will be recorded on eCRFs. The investigator is responsible for ensuring that all AEs observed by the investigator or reported by the subject that occur from the time that the subject has signed the informed consent through the end of the study are properly assessed, recorded, and reported as defined and described in the Adverse Events Section (12.0) of this protocol. All AEs must be assessed by the study investigator and properly documented by completing the subject's medical records (source documents) and appropriate eCRF. Additional documentation may be requested by the Sponsor, including but not limited to, a written subject narrative detailing the clinical course of the AE, a copy of any correspondence with the local EC/EB, and extracts from medical records (patient identifiers removed). All AEs will be monitored until they are adequately resolved or explained.

Table 8: AE Reporting Requirements

Type of Adverse Event	Reporting Requirements
Non-Serious and Anticipated Adverse Events	Report to Sponsor within 7 days of awareness
Serious Adverse Events	Report to Sponsor within 24 hours of awareness
Unanticipated AEs	Report to Sponsor within 24 hours of awareness
Subject Death	Report to Sponsor within 24 hours of awareness

The Sponsor will confirm that (serious) AEs are reported as required to the:

- **To Institutional Review Board (or equivalent):** The site is responsible for ensuring that all (serious) AEs are fully recorded and reported to the IRB (or equivalent) according to the local requirements.

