- **To Global Safety Monitoring Committee (GSMC):** The sponsor will forward all reported SAEs to the GSMC. The GSMC will evaluate whether the event is unanticipated, the seriousness, the relationship with/to the OAT (as applicable), and the perceived risk for the other study centers. The GSMC will determine whether the event is drug-related. Additional detail regarding the GSMC is provided in the Study Management Section (15.0) of this protocol.

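### In this unblinded trial no one is assigned to classify primary-endpoint events masked to arm, and the safety committee's stated tasks and event feed do not fill the gap

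*Combined protocol and SAP*

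**What the plan says.** Section 8.1: "This is a prospective, multicenter, randomized (1:1), controlled, two-arm, unblinded, pilot study". The primary endpoint (10.1, repeated in 13.2) is a composite of stroke and major bleeding over 12 months: "focal neurologic deficit of presumed vascular origin lasting for ≥ 24 hours or resulting in death) or major hemorrhagic complication (major bleeding". Table 2 holds the working definitions, and it defines a minor bleed as any clinical bleed that is not major.

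On who judges events, section 12.5 says "All AEs must be assessed by the study investigator and properly documented". It then says "The sponsor will forward all reported SAEs to the GSMC", and describes the committee's questions: "The GSMC will evaluate whether the event is unanticipated, the seriousness, the relationship with/to the OAT (as applicable), and the perceived risk". Section 15.6 says "The GSMC is tasked with adjudicating severity and causality of adverse events", and on materials, "Sponsor or designee will collect and compile the information packets or listings for the GSMC to review". The same section allows the committee to review accumulated safety data.

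Section 13.7.1 plans Kaplan-Meier curves, a log-rank test and a Fisher exact test on the primary endpoint. It does not say whose classification of events enters the analysis. The core laboratory in 11.5 covers Holter data only, and the Physician Advisory Committee's list in 15.5 has no adjudication task.

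**The concern.** Investigators know whether the subject is taking OAT. That knowledge can influence which borderline events are counted: a bleed in a subject on OAT, or a transient neurologic complaint in a subject off OAT, is more likely to be read as the outcome expected in that arm. Because minor bleeds are whatever is left after major bleeds are removed, one judgement moves an event between the primary endpoint and a secondary one.

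The usual protection in an open-label trial is classification by people who do not know the arm. This plan has a committee and a flow of event packets, but no stated step in which endpoint status is decided, and no masking. With few events expected, even a small amount of arm-dependent classification would show in the estimates.

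**Working it through.** The plan gives no figure on this point to reproduce. The total of 100 subjects in 13.3 comes without event rate, power or margin. The check is therefore mainly a comparison of sections, followed by simple arithmetic on scale.

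**1. Is endpoint classification among the committee's tasks?**
- Section 12.5: whether the event is unanticipated, its seriousness, its relationship to OAT, and the risk for other centers.
- Section 15.6: severity and causality.
- Severity in this protocol (Table 5) is a mild/moderate/severe scale based on impairment and intervention. It does not separate stroke from non-stroke or major from minor bleeding as Table 2 does.
- Result: classification against Table 2 is not listed anywhere, and no section masks any reviewer.

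**2. Must a primary event reach the committee?**
- The forwarding rule in 12.5 covers SAEs; 15.6 speaks of adverse events in general. The two differ in scope.
- Table 2 makes a bleed major if any one criterion is met. These include a hemoglobin fall of at least 2.0 g/L and symptomatic bleeding at listed sites such as the gastrointestinal tract, eye or joint.
- The SAE definition in 12.1 rests on death, life-threatening illness, permanent impairment, admission, or intervention to prevent permanent impairment. An emergency visit without admission does not by itself qualify.
- Result: a bleed can be major under Table 2 without being serious under 12.1, and nothing then requires it to be forwarded.

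**3. Who makes the endpoint call?** No section says. The investigator's assessment of every AE (12.2 to 12.5) is the only described step that could supply it, and it is unmasked. This is inferred from the silence of the other sections.

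**4. How much judgement is involved?** Deficit duration, CT/MRI or autopsy typing of stroke, hemoglobin change and transfused units are largely objective. Deciding that a deficit is presumed vascular, or that bleeding at a critical site is symptomatic, is not. Section 13.7.1 adds to the uncertainty by counting any thromboembolic event, where 10.1 and 13.2 restrict that component to major events specified as stroke. A TIA or a non-cerebral embolus could be counted under one wording and not the other.

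**5. Scale.** Inputs: 50 per arm (13.3); major hemorrhage at 1.5 to 4.2 per 100 patient-years on anticoagulation, by age (5.1). Assumption: every subject contributes a full year.
- Effect of one event on an arm's proportion: 1/50 = 2 percentage points.
- Expected major bleeds in a fully anticoagulated arm: 50 × 0.015 = 0.75, to 50 × 0.042 = 2.1.
- Exact (Clopper-Pearson) 95% upper limits for 0, 1 and 2 events in 50: 7.1%, 10.6% and 13.7%. Each added event raises the limit by about 3 points.
- Two-sided Fisher test with no events in one arm: 5 in the other gives p = 0.056 and 6 gives p = 0.027. At the expected bleed counts, one reclassified bleed would change the estimate and interval, not the outcome of the test.

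Follow-up shorter than a year, which 9.6 and 11.3 make likely by discontinuing subjects at AF recurrence, would lower these counts. Strokes would add to them, but the plan gives no stroke rate for subjects free of AF after ablation.

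**The case against.** Five arguments deserve weight.

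- *It is an unpowered pilot.* Section 13.3 disclaims statistical inference. That limits the consequence. But 13.1 states a non-inferiority aim and 13.7.1 plans tests and intervals on this endpoint, and a larger sample would not remove classification bias.
- *The criteria are largely objective.* This stands in part. It reduces the room for bias but does not cover the terms that need judgement.
- *The biases may cancel.* Up-grading bleeds on OAT and neurologic symptoms off OAT adds events to both arms, so the composite may be partly protected. This stands: neither the net direction nor its size can be stated. Cancellation cannot be relied on either, and the components would still be distorted.
- *Most primary events will be serious.* A stroke lasting a day, or a bleed at a critical site, will usually qualify as an SAE. The leak is therefore probably small, and the documents do not allow it to be quantified. Events that do arrive are still not reviewed for endpoint status.
- *A separate charter may assign the task.* Possibly, but these documents refer to none.

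A reader might also infer that the committee sees nothing but SAEs. The documents do not say so: 12.5 requires SAEs to be forwarded without excluding other events, and 15.6 speaks of adverse events generally.

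**Conclusion.** The gap is real and worth closing, but it does not invalidate the pilot. The plan has no stated step in which anyone masked to arm decides whether an event meets the primary endpoint, and 12.5 and 15.6 disagree on which events the committee handles. The scale is 2 percentage points per reclassified event against an expected 0.75 to 2.1 major bleeds per arm, assuming a full year of follow-up at the rates in 5.1.

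Two stronger conclusions are tempting and are not supported. The first is that the plan leaves the endpoint to the sites: it does not name the classifier, and site classification is only the most plausible reading. The second is that misclassification would favor a particular arm or reverse the result: the likely biases act in both arms, and at the expected bleed counts a single reclassified bleed would not change the Fisher test.

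**What to change.** 1. Reconcile 12.5 with 15.6 so that every suspected stroke, TIA, other thromboembolic event (including non-cerebral emboli) and bleeding AE goes to the existing committee, serious or not.
2. Step 1: the committee classifies each event against the protocol's endpoint definitions from packets with arm, OAT and INR redacted, before it sees any by-arm accumulated data on that event. INR must be redacted because Table 3 schedules it only for the OAT arm, so its presence reveals the allocation.
3. Step 2: the arm is disclosed for causality, which 12.2 ties to use or discontinuation of OAT and which therefore cannot be judged masked.
4. State in 10.1 and 13.7.1 that the masked committee classification defines the primary endpoint. Reconcile the restriction to stroke in 10.1 and 13.2 with the wider thromboembolic wording in 13.7.1, so that the committee has one definition to apply.

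The cost is protocol wording, redaction of packets that the sponsor or designee already compiles, and additional packets for non-serious bleeds. Treatment, visits and sample size do not change. Masking will be imperfect, since the clinical account of a bleed can reveal whether the subject was anticoagulated. The step cannot correct events that are sought or reported differently between the arms, because an unreported event never reaches the committee.

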16.0 Regulatory / Ethical Considerations

16.1 Basic Principles and Standards

This clinical study will be conducted according to applicable regulatory requirements and good clinical practice (GCP) guidelines including but not limited to:

- ISO 14155:2011 “Clinical investigation of medical devices for human subjects – Good clinical practice 21 CFR
- Declaration of Helsinki
- ICH E6 Good Clinical Practice
- Medical Device Directive 93/42/EC
- MEDDEV 2.12-1 Guidelines on a Medical Devices Vigilance System

16.2 Record Retention and Archiving

Each site will be asked to maintain study records for at least two years after the study is completed unless otherwise instructed by local requirements. The Sponsor will maintain study records according to the applicable Biosense Webster procedures.

Appendix A: Commonly Prescribed Oral Anticoagulation and Antiplatelet Therapies

In all countries, apart from Germany, any commercially available OAT may be prescribed.

In Germany only patients who are prescribed therapies included on the following list may be included in this study.

Anticoagulation Medications

Warfarin sodium

Dabigatran etexilate mesilate

Rivaroxaban

Phenprocoumon

Antiplatelet Medications

Clopidogrel hydrochloride

Clopidogrel besilate

Clopidogrel hydrogen sulphate

Prasugrel hydrochloride

Ticagrelor

Acetylsalicylic acid
